Total HDL particles, (μmol/L)	0.4	0.61	6.51	<0.0001	0.07
HDL particle size, (nm)	0	0.3	1.16	<0.0001	0.049
Large HDL particles, (μmol/L)	4.11	0.02	30.71	<0.0001	0.03
hs-CRP, (mg/L)	-22.4	0.0002	-28.4	<0.0001	0.67
ALP, (U/L)	-3.23	0.03	-11	<0.0001	<0.001

Results expressed as median percentage change from baseline. Source: RVX000222 data on file. Modified intention to treat population, 2-sided van Elteren test of RVX000222 vs. placebo, stratified by trial. Wilcoxon signed-rank test for within group comparison vs. baseline.

The data from all three individual Phase 2 studies in CVD patients showed independent, consistent trends for fewer MACE in RVX000222-treated subjects versus subjects receiving placebo. In the ASSERT study, 2.2% of subjects treated with RVX000222 experienced a MACE compared to 2.7% of placebo-treated subjects during 12 weeks of therapy. In the SUSTAIN study, MACE occurred in 7.5% of placebo-treated subjects and only 0.4% of RVX000222-treated subjects ($p < 0.06$) after 24 weeks of therapy. This trend was also observed in the ASSURE trial, with 14.3% of placebo-treated subjects experiencing MACE compared to 7.5% of subjects in the RVX000222-treated group after 26 weeks of therapy, an approximately 48% difference ($p < 0.1$).

Given the promising findings of reduced MACE from these three studies, a post-hoc meta-analysis was conducted using the pooled data ($n = 798$). Collectively, there was a statistically significant ($p = 0.023$) reduction in MACE as defined by death, myocardial infarction (MI), coronary revascularization, or cardiovascular hospitalization (CV) as shown in Figure 1. Subjects receiving RVX000222 were 44% less likely to experience a MACE compared to placebo with only 5.9% of RVX000222-treated subjects experiencing any MACE compared to 10.4% for placebo-treated subjects. Approximately 80% of subjects were treated with high intensity statin therapy (atorvastatin and rosuvastatin).

[figure not shown]

Figure 1: MACE in Subjects Treated in RVX000222 Phase 2 Studies

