4.0 STUDY DESIGN

This is a double-blind, placebo-controlled, 2-arm parallel-group (allocation ratio 1:1), study of RVX000222 at a daily dose of 100 mg b.i.d. (total daily dose of 200 mg) or matching placebo in combination with high intensity statin therapy administered to T2DM subjects with history of recent CAD event and HDL-C level $<$ 40 mg/dL in males or $<$ 45 mg/dL in females.

After an initial screening period of 1 to 2 weeks during which subjects will demonstrate tolerance of high intensity statin therapy, subjects will be randomized to either RVX000222 100 mg b.i.d. or matching placebo with continued statin treatment. This combination treatment period will continue until 250 narrowly defined MACE events have occurred in the study and all surviving patients have been followed for at least 24 weeks from randomization. Blinded treatment with RVX000222 or matching placebo will then be discontinued. Subjects will remain on high intensity statin therapy for 4 more weeks until the Follow-Up Visit.

The study is an event-based trial and will continue until 250 primary endpoint events have occurred. Study treatment will be terminated after the 250th adjudicated event occurs. At that time, all subjects actively treated will conduct their Last Visit on Treatment and then be discontinued from investigational drug. Subjects will then return 4 weeks after last day of treatment for the Follow-Up Visit.

A Clinical Steering Committee (CSC) will oversee the conduct of the study. A Data Safety Monitoring Board (DSMB) will oversee the safety data for this study and independent CEC will adjudicate all suspected MACE composite events in an ongoing manner. An independent team (including an independent statistician) will perform the prospective unblinded analyses described in Section 10.8 (Data Safety Monitoring Board) and will report the results to the DSMB. Each committee will develop a charter to describe their activities and responsibilities prior to initiation of the study.

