5.2 Inclusion Criteria

Subjects who meet the following criteria may be enrolled:

1. Male and female subjects age 18 and over with documented diagnosed T2DM and a CAD event of either unstable angina or myocardial infarction, not less than 7 days and no more than 90 days prior to Visit 1. In order to have sufficient number of clinical events, the number of subjects with unstable angina will be limited to 25% of the total number of subjects.

- Unstable angina: for a qualifying unstable angina event, each of components (a), (b), and (c) must be satisfied:
 - a. Characteristic ischemic pain or discomfort in chest or associated referral areas, occurring at rest or with minimal exertion
 - b. ECG changes consistent with acute myocardial ischemia based upon at least one of the following:
 - i. new or presumed new ST elevation
 - ii. new or presumed new ST depression
 - iii. new or presumed new T-wave inversion
 - c. Objective evidence of obstructive coronary artery disease based upon at least one of the following:
 - i. new or presumed new evidence of myocardial ischemia or infarction by perfusion imaging
 - ii. new or presumed new regional wall motion abnormality
 - iii. current evidence of at least one epicardial coronary artery stenosis $\geq 70\%$ by coronary angiography
 - iv. need for coronary revascularization for the index ACS event, including percutaneous coronary intervention (PCI) with or without coronary stenting
 - Previous MI 7-90 days before screening, treated with or without a percutaneous coronary intervention (PCI). For a qualifying event of MI, **two of the following three criteria must be satisfied**:
 - a. Characteristic ischemic chest pain or pain in associated referral areas
 - b. Dynamic elevation of troponin T or I or CKMB, if troponin T or I is unavailable at the local lab (at least above the upper limit of normal for the laboratory)
 - c. Development of new Q-waves in at least two adjacent ECG leads, or development of a new dominant R wave in V1
2. Documented diagnosis of T2DM (one or more of the following criteria must be met):
 - Documented history of T2DM
 - History of taking diabetes medication
 - HbA1c $\geq 6.5\%$ at Visit 1
 3. For males HDL-C of <40 mg/dL (1.04 mmol/L) and for females HDL-C of <45 mg/dL (1.17 mmol/L) at Visit 1.
 4. In the opinion of the Investigator, subjects currently not on high intensity statin therapy will be able to start rosuvastatin according to the protocol at Visit 1.

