7.2.2 Study Visit 2/Randomization (Week 0)

- Review inclusion and exclusion criteria
- Record any AEs
- Record concomitant medications
- If subject satisfies all inclusion and exclusion criteria, randomization may occur
- Measure vital signs
- Collect clinical laboratory test samples: liver safety panel
- Collect biomarker laboratory test samples in a selected subset of subjects: lipoproteins, fasting insulin, and inflammation panel
- Collect serum/plasma archive samples
- Collect blood samples for pharmacogenomic testing (DNA and RNA) if subject consent received
- Perform MOCA test for any subjects ≥ 70 years of age at randomization
- Administer EQ-5D-5L
- Dispense investigational drug
- Dispense high intensity statin

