7.2.6 Study Visits 8 (Weeks 12)

- Collect clinical laboratory test samples: liver safety panel
- Collect biomarker laboratory test samples in a selected subset of subjects: inflammation panel
- Collect serum/plasma archive samples
- Record concomitant medications
- Monitor AEs
- Perform drug accountability; dispense investigational drug; dispense high intensity statin

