3.2.3. Exploratory Endpoints

- The percent change in hsCRP, fibrinogen, and inflammatory cytokines within and between treatment groups
- Change in MoCA score in all and those with baseline MoCA < 26 within and between treatment groups
- Transcription/mRNA change in whole blood from baseline to 6 weeks treatment within and between treatment groups
- Change in Health Related Quality of Life (HRQOL) as measured using the EQ-5D-5L

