6.2. Baseline Disease Characteristics and Medical History

Baseline disease characteristics such as time since diagnosis of T2DM to randomization, index ACS event type, and time from ACS to randomization will be calculated or extracted from medical history and presented by treatment group.

Medical history will consist of any significant conditions or diseases that stopped at or prior to the date of informed consent. Ongoing conditions will be considered concurrent medical conditions.

Concurrent medical conditions are significant ongoing conditions or diseases present at time of informed consent. These include clinically significant laboratory findings, ECG, or physical examination abnormalities. Summaries of medical history and concurrent medical conditions will be based on the FAS.

Medical history and concurrent medical conditions will be coded using the latest possible version of Medical Dictionary for Drug Regulatory Activities (MedDRA).

7. Treatments and Medications

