8.4. Other Secondary and Exploratory Analysis

Other secondary and exploratory endpoints are listed in [sections 3.2.2.1](#) and [3.2.3](#). Quantitative endpoints that are defined as a (percent) change from baseline will be analyzed using analysis of covariance (ANCOVA) models with treatment group, baseline value, and strata as covariates. Descriptive statistics for (percent) change from baseline at each post-baseline visit will be summarized using the FAS.

Descriptive statistics (number of subjects with non-missing values, mean, standard deviation, minimum, 25th percentile, median, 75th percentile, and maximum) will be used to summarize continuous variables by treatment group for the FAS set.

Least squares (LS) means and difference in LS means between RVX000222 and Placebo with standard errors (SEs) and 2-sided 95% CI and p-values obtained from ANCOVA model will be presented at each applicable post baseline visit.

Mixed-effects model repeated measures analysis will be used to model percent change in measurements over time at the last visit on treatment (LVT). An unstructured covariance matrix will be used to fit the underlying MMRM model. Subject and error will be considered random effects; all effects that include treatment, strata and baseline value will be considered fixed.

The pattern of change from baseline over time will also be displayed graphically in Figures for some endpoints. No multiplicity adjustment is planned to test the other secondary and exploratory endpoints. Since most of the other secondary endpoints are clinical laboratory tests, they are also summarized under safety analysis in [section 9](#).

Analyses will summarize EQ-5D-5L scale and subscale scores at each visit and change from baseline at each visit.

Analyses will address mean differences by treatment group on MOCA scale and differences for subjects with a baseline score indicative of cognitive impairment (Baseline MoCA < 26)

9. Safety Analysis

Safety data such as clinical laboratory results, vital signs, findings from physical examinations will be listed and/or summarized by treatment group where appropriate. No inferential hypothesis testing will be performed on the safety variables.

The assessment of safety will be based on the frequency, intensity, and types of AEs and for change and from Baseline in the clinical laboratory variables, and vital sign measurements.

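### The ANCOVA for the inflammation markers omits time since the index coronary event, a variable the trial already derives; this costs some precision but does not bias the comparison

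*SAP*

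**What the plan says.** **Timing.** Protocol 5.2 requires the qualifying event to be "not less than 7 days and no more than 90 days prior to Visit 1". Protocol 4.0 randomizes "After an initial screening period of 1 to 2 weeks". The inflammation panel is first drawn at randomization (Protocol 7.2.2: "Collect biomarker laboratory test samples in a selected subset of subjects: lipoproteins, fasting insulin, and inflammation panel") and next at Week 12 (Protocol 7.2.6: "Collect biomarker laboratory test samples in a selected subset of subjects: inflammation panel"). The Schedule of Events adds a Week 52 sample and none after that. SAP 9.2.6 caps the biomarker subset at 600 subjects.

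**Endpoint.** SAP 3.2.3 lists, as exploratory, "The percent change in hsCRP, fibrinogen, and inflammatory cytokines within and between treatment groups".

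**Model.** SAP 8.4 specifies ANCOVA "models with treatment group, baseline value, and strata as covariates". It reports least-squares means and their difference from placebo, with standard error, confidence interval and p-value, at each applicable visit. The strata are country and statin (SAP 4.3.1 and 8.2).

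**The omitted variable.** Under SAP 6.2, "time from ACS to randomization will be calculated or extracted from medical history" for presentation by arm. Its only analytic use is in SAP 8.2, as a subgroup of the primary endpoint split at 30 days.

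**The concern.** The three markers belong to the acute-phase response, and subjects enter at very different distances from an acute event. Suppose the markers are still coming down in early entrants and have levelled off in late ones. Two subjects with the same baseline hsCRP, one sampled at 2 weeks and the other at 15 weeks, would then have different expected Week 12 values. A model with only baseline and strata cannot separate them, so the difference goes into the residual.

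Two things are at stake, both modest. The between-arm comparison is less precise than it could be at no cost. And because the endpoint also names change within each arm, a fall in the RVX000222 arm alone could include recovery from the index event. The panel matters for interpretation because Protocol 1.0 attributes the drug's likely action more to inflammatory and related pathways than to lipids.

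**Working it through.** The documents give no power, variance or effect size for the inflammation endpoints, so there is no plan figure to reproduce.

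**Step 1: when the samples fall.**
- Earliest baseline: 7 + 7 = 14 days after the event (2.0 weeks).
- Latest baseline: 90 + 14 = 104 days (14.9 weeks).
- Week 12 sample, nominally: 14 + 84 = 98 days to 104 + 84 = 188 days.

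**Step 2: what the covariate would buy.** The documents give no post-ACS course for any marker, so the following values are assumptions:
- Log marker = stable subject level (SD 0.9) + acute excess + within-subject noise (SD 0.5).
- Excess at day t = A × exp(−(t − 14)/τ), with A from 0.5 to 1.5 log units and τ from 15 to 30 days.
- Days from event to baseline uniform over 14 to 104, and no drug effect.

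Large simulated samples were fitted with and without log(days since event), next to baseline. R is the resulting proportional fall in residual variance. The equivalent number of extra subjects is 600 × (1/(1 − R) − 1).

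| Week 12 outcome | R | Extra subjects in 600 |
|---|---|---|
| Percent change, raw baseline as covariate | about 1.2% to 8.6% | 7 to 56 |
| Percent change, log baseline as covariate | about 0.9% to 5.8% | 5 to 37 |
| Change in log marker | about 1.6% to 12.3% | 10 to 84 |

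For example, 600 × (1/0.914 − 1) = 56 and 600 × (1/0.991 − 1) = 5. The first two rows match the planned scale. A 9% fall in variance narrows the confidence interval by 1 − √0.91 = 4.6%; a 1% fall narrows it by 0.5%.

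**Step 3: sensitivity and validity.** A second set of assumptions used within-subject SD 0.6, an excess of 1 to 3 log units extrapolated to the day of the event, and τ of 14, 30 or 60 days. It was run on the log scale with 600 subjects allocated 1:1 and 3,000 trials per setting. The variance of the treatment contrast fell by 0.3% to 10.9%, worth 2 to 73 subjects. With no acute excess there was no gain (−0.2%). With or without the covariate, bias was at most 0.002 log units and type I error was 0.045 to 0.056.

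**Step 4: change within an arm, no drug effect.** Under the Step 2 assumptions the median percent change to Week 12 is a fall of 8% to 35%. The mean percent change, which ANCOVA on that scale estimates, runs from +19% to −13%, because percent change in a skewed marker is pulled upward. Even the sign of a mean within-arm change therefore depends on the assumptions.

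**The case against.** The best defence is that the plan is valid as written. Allocation is randomized, so time since the event is balanced in expectation, and Step 3 shows no bias and no inflation of type I error. The difference from placebo is already specified, nothing in the SAP says that a fall in one arm alone will be read as a drug effect, and the endpoint is exploratory and outside multiplicity control. All of that stands. What remains is a prognostic variable, already in the database, that the model does not use.

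Four stronger readings are tempting, and the documents support none of them:
- **That the treatment comparison is confounded by recovery.** Randomization and Step 3 rule this out.
- **That the markers are known to be still settling at baseline.** This is plausible for early entrants and less certain near 15 weeks. The documents contain no data on it.
- **That Table 2 of the protocol demonstrates such recovery.** Its footnote reads "Results expressed as median percentage change from baseline", and placebo hs-CRP fell 22.4% (p = 0.0002 against baseline) with p = 0.67 between arms. Those subjects had stable CAD and/or dyslipidemia, so that fall is not evidence of recovery from a recent index event. It shows only that change within an arm is a poor guide to drug effect in this programme.
- **That the MMRM needs the same change.** SAP 8.4 aims it at the last visit on treatment, where the panel is not drawn, and SAP 8 limits MMRM to a subset of secondary outcomes.

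**Conclusion.** The point holds as a low-priority improvement in efficiency. The facts about timing, model terms and the derived interval come directly from the documents. The size of the gain does not: it rests on assumed recovery curves and is about 1% to 9% of residual variance on the percent-change scale, or roughly 5 to 60 subjects in a full subset of 600. It is close to zero if the excess is small or gone by randomization. The calculation covers Week 12 only; the Week 52 gain was not computed.

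A reader might also infer that the covariate would make change within an arm interpretable. It would not, because adjustment does not remove a shift common to both arms; only the contrast with placebo does. No primary or key secondary result is affected.

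**What to change.** In SAP 8.4, for hsCRP, fibrinogen and cytokines only, add log(days from index ACS to randomization) to the Week 12 and Week 52 ANCOVA, using the interval already derived under SAP 6.2. Add a sentence saying that the inflammation conclusion rests on the placebo-adjusted difference and that changes within an arm are descriptive. The second sentence is mainly clarification, since the contrast is already planned. Leave the MMRM as it is.

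The same edit could align SAP 8, which gives the ANCOVA without strata, with SAP 8.4, which includes them.

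The cost is two sentences, one model term and one degree of freedom per model. No new data are needed. The change should be made before unblinding.

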9.1. Adverse Events

Adverse events will be summarized using the safety set. Adverse events will be coded using MedDRA (version 17.0 or higher), summarized by frequency, severity, relationship to study drug, and number of subjects per treatment and by the preferred term and system organ class. Data will be summarized using preferred term and primary system organ class. The coded events will be summarized by treatment group, in subsets of all treatment-emergent AEs, all treatment-related AEs, and serious treatment emergent AEs.

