Data Safety Monitoring Board	
An independent DSMB will be appointed to monitor the subject safety data on an ongoing basis at quarterly meetings during the course of the study. The ongoing DSMB safety review will include review of adverse events of special interest, including all opportunistic infections and serious infections. In addition to ongoing safety assessments, the DSMB will review and interpret the planned interim efficacy analysis to assess futility and sample size, if indicated, when 75% (i.e. 188) of the 250 narrowly defined MACE have been confirmed by CEC.
 
The statistical methodology for SSA that preserves the overall Type I error will be described in greater detail in the DSMB interim futility / sample size adjustment analysis plan.

Sample Size	
It is estimated that enrollment of approximately 2400 subjects will be needed to reach the 250 narrowly defined MACE in this event based trial.

Statistical Considerations	
Sample Size Justification:
 
A sample size of 2400 randomized subjects will yield approximately 80% power for the primary analysis under the following assumptions:
 
 1. Total number of events: 250 2. 2-sided type 1 error rate of $\alpha=5\%$ 3. 10.5% event rate in the placebo arm at 18 months 4. 30% relative risk reduction (7.47% event rate at 18 months in the RVX000222 arm) 5. A cumulative drop-out rate of 10% per arm by the end of the study (5% drop out rate per arm by year 1) 6. Provision for an interim analysis to terminate the trial for futility (non-binding) when approximately 75% of the 250 events have occurred 
Primary Analysis:
 
The primary analysis of time to the first occurrence of MACE narrowly defined will be completed following the occurrence of the 250th adjudication-confirmed primary endpoint event. The RVX000222 and placebo groups will be compared using a two-sided stratified log-rank test with an alpha = 0.05 level of significance.
 
Secondary and Exploratory Analyses:
 
Endpoints that are defined as time-to-event variables will be analyzed using the stratified log-rank test, as described for the primary analysis. Quantitative endpoints that are defined as a change from baseline will be analyzed using analysis of

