8.2.4 Adverse Events of Special Interest

Adverse events of special interest (AESIs) in this study are AEs which could be associated with immunosuppression, including all opportunistic infections and any serious infections that occur during the AE reporting period. The study Medical Monitor will review AESIs on an ongoing basis in a blinded fashion, and the DSMB will periodically review unblinded AESIs at their regular meetings.

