9.7 Safety Analysis

Drug administration, disposition data, medical history and prior medications will be summarized by treatment group using descriptive statistics. Safety data such as clinical laboratory results, vital signs, findings from physical examinations, and MOCAs will be listed and summarized by treatment group where appropriate. For continuous variables, these summaries will include sample size, mean, median, standard deviation, minimum, and maximum. For categorical variables, these summaries will include frequencies and corresponding percentages. No inferential hypothesis testing will be performed on the safety variables.

The assessment of safety will be based on the frequency, intensity, and types of AEs and for change and shift from Baseline in the clinical laboratory variables, and vital sign measurements. Baseline values for clinical laboratory variables, and vital sign measurements are defined as the last non-missing values obtained prior to dosing. Clinical laboratory variables outside reference ranges will be flagged in clinical laboratory listings.

Adverse events will be summarized using the safety set. Adverse events will be coded using MedDRA (version 17.0 or higher), summarized by frequency, severity, relationship to study drug, and number of subjects per treatment and by the preferred term and system organ class. Data will be summarized using preferred term and primary system organ class. The coded events will be summarized by treatment group, in subsets of all treatment-emergent AEs, all treatment-related AEs, non-serious treatment emergent AEs and serious treatment emergent AEs. Adverse events of special interest (opportunistic infections and all serious/severe infections) will be analyzed as a subset of the overall AEs. Treatment-emergent AEs will be defined as any AEs, regardless of relationship to study drug, that occur after the first dose of double-blind investigational drug and within 14 days after the last dose of double-blind investigational drug. Treatment-related AEs will be defined as any AEs that are considered by the investigator to be either possibly, probably, or definitely related to study drug. In addition, if relationship information is missing, the AE will be considered treatment-related. Listings for the subsets of SAEs and treatment-related SAEs will be provided.

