9.1.1. Incidence of Adverse Events

A Treatment-Emergent AE (TEAE) will be defined as any AEs, regardless of relationship to study drug, that occur after the first dose of double-blind study drug and within 14 days after the last dose of double-blind study drug. An AE with a reported onset date after the subject has signed the informed consent document and before the date of randomization (or the date of first dose of study drug if a subject was treated but no randomized) will be considered a pre-study event. AEs with missing onset dates will be considered on-study events.

If the day of onset of an AE is missing, and if the month and year of an onset date are on or after Day 1, general imputation rules from [section 4.5](#) will be applied.

If, despite implementing the above conventions, the onset date of the AE cannot be placed before, on, or after Day 1, then the event will be considered on-study.

All AEs will be coded using the MedDRA Version 17.0 or higher coding system. In this dictionary, each diagnosis is mapped to a lower level term and then to a preferred MedDRA term, which is then mapped to a system organ class.

TEAEs will be summarized by treatment group and overall for the SS. Summaries of TEAEs will be displayed by descending overall frequency for system organ class and preferred term. Treatment-Emergent AEs and SAEs will include events per 100 subject-years of study drug exposure. In addition, TEAEs leading to Study Drug Discontinuation, Serious TEAEs and TEAEs resulting in Deaths will be presented.

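### SAP 9.1 omits, without a stated reason, the analysis of adverse events of special interest that protocol 9.7 promises, and the protocol describes the infections concerned in two ways

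*SAP*

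**What the plan says.** **The analysis.** Protocol 9.7 summarises coded adverse events by treatment group in four subsets: treatment-emergent, treatment-related, non-serious treatment-emergent and serious treatment-emergent. It then adds: "Adverse events of special interest (opportunistic infections and all serious/severe infections) will be analyzed as a subset of the overall AEs". SAP 9.1 follows the same paragraph closely, keeps three of the four subsets and ends there: "The coded events will be summarized by treatment group, in subsets of all treatment-emergent AEs, all treatment-related AEs, and serious treatment emergent AEs". The SAP contents list runs from 9.1.1 to 9.1.7 with no AESI section. Its abbreviation list has no AESI entry, although the protocol's does. The supplied SAP text nowhere mentions AESIs or opportunistic infections.

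**The definition.** Protocol 8.2.4 defines AESIs as adverse events that could be associated with immunosuppression, "including all opportunistic infections and any serious infections that occur during the AE reporting period". The DSMB row of the protocol synopsis also names two types: "review of adverse events of special interest, including all opportunistic infections and serious infections". Section 9.7 alone adds severe infections.

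**The window.** Protocol 8.2 collects adverse events from consent to the end of the study, and protocol 6.10 keeps subjects who stop drug in the study for all remaining visits. SAP 9.1.1 defines treatment-emergent events as those "that occur after the first dose of double-blind study drug and within 14 days after the last dose of double-blind study drug". Protocol 9.7 uses the same limit: "within 14 days after the last dose of double-blind investigational drug".

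**Precedence.** Protocol 9.1 allows the SAP to modify and override the protocol's statistical methods.

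**The concern.** Immunosuppression is a risk that the sponsor took trouble over. It drives exclusion 7 and is named again in exclusion 18. It is the only category designated an AESI, it is a standing item for the DSMB (protocol 10.8), and immunosuppressant use is one of the four major protocol violations expected in SAP 5.2. A programmer working from the SAP nevertheless has no instruction to group these events or compare them between arms.

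Opportunistic infections are the weak spot. Each is likely to be coded to its own preferred term, so a difference between arms could be spread over many sparse rows. If the grouping is built only after unblinding, the choice of terms is open to influence from the results. With two descriptions in the protocol and none in the SAP, the DSMB reports and the final report could count different events under the same name.

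**Working it through.** No stated figure is in dispute. Steps 1 to 3 compare text; step 4 sizes the time that the SAP's main tables do not cover.

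1. **Is the AESI analysis in the SAP?** Protocol 9.7 has four subsets plus the AESI sentence. SAP 9.1 has three subsets and no AESI sentence. Incidence (SAP 9.1.1), causality (9.1.2) and intensity (9.1.3) are tabulated by system organ class and preferred term. An organ-class row mixes opportunistic with ordinary infections, and a preferred-term row separates one opportunistic infection from the next. No planned row pools them.

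2. **Do the definitions agree?** Intensity (protocol 8.2.2.2: mild, moderate, severe) and seriousness (8.2.3.1: death, hospitalisation and so on) are separate scales. An infection that is severe, non-serious and non-opportunistic is therefore named in 9.7 but not in 8.2.4 or the synopsis. Section 8.2.4 is also open, with the infections given as examples, while the bracket in 9.7 reads as a closed list. Neither document lists the terms that identify an opportunistic infection.

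3. **Do the windows agree?** Section 8.2.4 covers the whole reporting period, and 9.7 ties the AESI analysis to all adverse events, not to treatment-emergent ones. The SAP's main tables are of treatment-emergent events. An opportunistic infection on day 20 after last dose in a subject still under follow-up is an AESI under 8.2.4, but it is outside those tables.

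4. **How much time is outside?** Inputs: uniform accrual over 1.7 years and total duration 2.75 years (SAP 4.2); follow-up visit 4 weeks after treatment ends (protocol 4.0); 14-day limit (SAP 9.1.1).

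- Subject who completes treatment: 28 − 14 = 14 of 28 days after last dose (50%). One synopsis sentence allows up to 16 weeks, which gives 112 − 14 = 98 of 112 days.
- Mean potential follow-up, ignoring events and drop-out: 2.75 − 1.7/2 = 1.90 years, × 365.25 = 694 days (99 weeks).
- Early stopper, with stopping times uniform over follow-up: 694/2 + 28 − 14 = 361 days outside.
- The documents give no discontinuation rate, so a share d of 5% to 30% is **assumed**. Mean days outside = d × 361 + (1 − d) × 14, over 694 + 28 = 722 days observed.

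| Assumed share stopping early | Mean days outside per subject | Share of observed time |
|---|---|---|
| 5% | 18.05 + 13.3 = 31 | 4.3% |
| 10% | 36.1 + 12.6 = 49 | 6.7% |
| 20% | 72.2 + 11.2 = 83 | 11.6% |
| 30% | 108.3 + 9.8 = 118 | 16.4% |

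If the last 28 days lie inside the 2.75 years, an early stopper has (694 − 28)/2 + 14 = 347 days outside. The ends of the range become (0.05 × 347 + 0.95 × 14)/694 = 4.4% and (0.30 × 347 + 0.70 × 14)/694 = 16.4%. These are shares of time, not counts of AESIs.

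**The case against.** **The SAP is silent; it does not cancel the commitment.** Protocol 9.7 still stands, protocol 9.1 asks for other method changes to be explained in the clinical study report, and the table shells mentioned in SAP 4.1 are not available here. This is fair. A reader might infer that the sponsor decided against the analysis, and the documents do not show that. They do show a governing plan without it and no explanation.

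**Much remains visible.** Serious treatment-emergent events are presented by arm, by system organ class and preferred term, so on-treatment serious infections can be seen. SAP 4.1 lists all eCRF data, and SAP 9.1.7 reports all deaths. Events leading to drug withdrawal (9.1.6) and serious-event rates per 100 subject-years (9.1.1) are not clearly limited to the 14-day window. This stands and narrows the gap to the pooled AESI count, chiefly of opportunistic infections.

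**Monitoring is intact.** The medical monitor reviews AESIs blinded, and the DSMB reviews them unblinded at its quarterly meetings (protocol 8.2.4, 10.8). This also stands: the gap is in the final analysis only.

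**The 14-day limit is sound.** It is the same in both documents. With a half-life of about 11 hours (protocol 1.0), 14 days is 14 × 24/11, or about 30 half-lives. The limit suits on-treatment reporting and is not an error. What remains is that 8.2.4 and 9.7 set a wider frame for AESIs, which no SAP table fills.

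**The definitions need not conflict.** Because 8.2.4 is open, it does not rule out severe non-serious infections. That softens the difference, but an open definition without a term list still leaves the count undetermined.

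**Conclusion.** The point holds in a limited form. The SAP as written has no planned by-arm count of the AESI group in the final analysis, contrary to protocol 9.7. The protocol's two descriptions of the infections could lead the DSMB and the final report to count different events.

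Two stronger readings are not supported. One is that the trial would be unable to detect any infection signal: on-treatment serious infections are tabulated by arm, and the underlying data are collected. The other is that immunosuppression is the only risk the protocol marks out: transaminase elevation is named as the dose-limiting toxicity (protocol 1.0) and has its own monitoring rules (6.10.1).

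No AESI rate is given, so the number of events affected cannot be estimated. The only size available is time outside the SAP's main tables, about 4% to 16% of observed time. It rests on the assumed 5% to 30% early discontinuation, uniform stopping times and no allowance for events or drop-out. The textual findings do not depend on it. The matter should be corrected before unblinding.

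**What to change.** Add an AESI subsection to SAP 9.1 and reconcile protocol 8.2.4, protocol 9.7 and the SAP:

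- **Definition:** one wording in all three places that keeps the open lead of 8.2.4 (adverse events that could be associated with immunosuppression). It should not be closed to two infection types.
- **Terms:** a preferred-term list, including the terms that count as opportunistic infections, fixed before unblinding.
- **Table:** subjects with at least one AESI, by arm, on the Safety Set, with rows for opportunistic infections, serious infections and severe non-serious infections.
- **Windows:** show the table twice, from first dose to 14 days after last dose and from first dose to last contact. The treatment-emergent definition stays as it is.

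The cost is SAP wording, an aligning edit to the protocol, one term list and two extra tables. The data are already collected, and no new procedures are needed.
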